1.1 Background

Obesity has reached epidemic proportions and is the biggest challenge our health care systems have to face both in terms of its personal and social deleterious consequences.

Lifestyle interventions including alterations in diet and increases in physical activity are effective in the short term only [1, 2]. Few pharmacological agents have been used for weight loss but unfortunately even fewer have survived the test of time.

The most effective treatment modality for obesity is obesity surgery which has sustainable weight loss effects over a 15 year period at least and also offers a mortality benefit [3]. The most popular surgical procedures used worldwide include the gastric bypass, gastric banding and the sleeve gastrectomy. These procedures cause weight loss primarily by reducing hunger and increasing satiety [4]. Bile has been implicated in the release of satiety gut hormones as well as a mediator of the metabolic effect of the operation [5].

In the last few years new pharmacological agents, also called Incretin therapies, have been introduced for the treatment of Type 2 Diabetes Mellitus. Exenatide, an Exendin 4 analogue and Liraglutide, a GLP-1 analogue, stimulate insulin secretion from the pancreas as part of their glucose reducing properties. They do however also have impressive weight reducing effects which is something unusual in the field of diabetes pharmacotherapy. They reduce food intake through their actions in the hypothalamus, by causing nausea -at least initially- and by reducing gastric emptying thus creating a sensation of fullness [6].

The EndoBarrier is fundamentally a gastrointestinal impermeable barrier or a gastric sleeve that prevents food from coming in contact with the intestinal wall. The device is implanted endoscopically through the mouth and is placed in such a way that it lines the first two feet of the small intestine. This helps to prevent easy absorption of food as long as it remains in the sleeve and has huge impact on the patients intake of nutrients and calories [7]. Research in animal models suggests that when the duodenum and proximal jejunum are surgically bypassed, the mid and distal jejunum is stimulated by undigested nutrients. The jejunum then signals to the brain to reduce hepatic glucose output [8]. In clinical studies, the EndobARRIER improves fasting and post prandial glycaemia via a reduction in insulin resistance, as measured by HOMA-IR (Homeostatic model assessment-Insulin Resistance) [9]. This is thought to be mediated by bile acids [10]. The HOMA-IR is a surrogate and imprecise marker of hepatic insulin resistance and the hyperglycaemic euglycaemic clamping method is the gold standard. Bile acids are believed to be key mediators behind these metabolic improvements. By confirming that the bypass of the proximal bowel reduces hepatic insulin resistance and hepatic glucose output, we can then begin to understand the mechanisms through which this device (and eventually bariatric surgery) improves glycaemia and even food preferences through the signalling of the jejunum to the brain.

Anecdotal evidence from the Obesity and Diabetes clinics and also limited data from the literature, suggest that patients after obesity surgery [11-15] but also patients on incretin therapies not only reduce their total intake of calories but also change the macronutrient composition of their diets. The most consistent change patients describe includes a reduction in the proportion of fat and sugars in their diets and an increase in the consumption of fruit and vegetable. Potential mechanisms causing this impressive shift in

food preferences include alterations in sensory perception of these macronutrients (i.e. changes in taste) or post ingestive effects. Elucidation of these mechanisms can lead to safer and more effective targeted pharmacological and surgical treatments for obesity.

There is lack of prospective studies comparing the above obesity surgical procedures and their effects on food preferences, satiety, gut hormones, bile acids and hepatic glucose output. There is no data on incretin therapies and food preferences in humans [16].

2. Study Objectives

The objective of this study is to investigate the effects of obesity surgical procedures and incretin therapies on food preferences, satiety, gut hormones, bile acids and hepatic glucose output in overweight and obese patients.

3. Study Design

This is a prospective observational controlled trial. 400 overweight and/or obese patients (Body Mass Index $\geq 30 \text{ Kg/m}^2$) will be recruited from the Imperial College NHS Trust, Royal Surrey County Hospital, Musgrove Park Hospital, King's College Hospital and private obesity and/or Diabetes clinics and studied prospectively for 1 year. The study groups will be as follows (n=50 per group):

- Group A: Patients due to undergo gastric bypass
- Group B: Patients due to undergo gastric banding
- Group C: Patients due to undergo sleeve gastrectomy
- Group D: Patients due to undergo endoscopic EndobARRIER insertion
- Group E: Patients due to be commenced on Exenatide
- Group F: Patients due to be commenced on Liraglutide
- Group G (control): Patients due to be commenced on a lifestyle intervention programme
- Group H (control): Patients due to have non bariatric surgery (i.e. cholecystectomy) or an elective diagnostic endoscopy

As part of routine care these patients will be seen by a qualified doctor or dietitian/nutritionist/diabetes specialist nurse (DSN) before and after intervention. Patients in control group G and H will be asked to use a low calorie diet either as part of their routine care or for research purposes only. Patients will be asked to prospectively complete food diaries on three consecutive days which are representative of their usual dietary intake and have a dietary assessment. This assessment will take 30-45 minutes and will take the form of a short discussion of dietary habits and will include completion of eating behaviour questionnaires (assessing dietary/personality traits including restraint, disinhibition, external eating and emotional eating). The first dietary assessment will be completed before the intervention and at 1 month, 3 months, 6 months and 12 months after intervention. Total energy intake and macronutrient composition comparisons pre and post intervention will form the basis of our analysis.

20 patients in each group will undergo more detailed measurements of food intake, hunger, satiety, gut hormones and bile acids. The research protocol will be the similar to that previously published by the Department of Metabolic Medicine, Imperial College, London. Participants will be fasted for 12 hours overnight and will attend for the study on 5 occasions. On each occasion venous blood samples will be taken and visual analogue scores will be measured over a 3 hour period using previously published methodology (Appendix Table 1: Test Periods). Samples or sample containers will be anonymised before collection but will be traceable back to the individual patients. Urine will be collected once. A qualified medical doctor will insert a venepuncture cannula into the arm of the patient and 5ml blood will be withdrawn at baseline, 15, 30, 60, 90, 120, 150 and 180 minutes following ingestion of a

standard 400kcal meal as below (Appendix Table 2: Protocol of each Test). After each sample the cannula will be flushed with saline to keep it patent. The protocol will be carried out 5 times per patient, pre intervention, 2, 7-30 days, 3 and 6-12 months post intervention. Plasma samples will be analysed for gut hormones as well as for primary bile acids and lipids. An extra blood and urine test will be obtained 1 month after treatment but not followed by a meal test.

Ten to twenty patients in each group (different from those taking part in the meal studies) will undergo measurements of hepatic glucose output/insulin resistance through euglycaemic hyperinsulinaemic clamps (Metabolic Study). Patients will be studied up to 4 times: at baseline, within 1-2 weeks of a low calorie diet and within 1-2 weeks after their weight loss treatment, whilst on the same liquid diet. The low calorie liquid diet is nutritious and contains all appropriate macronutrients. Such diets are frequently used as part of obesity interventions to reduce weight and risk. Patients will provide the investigators with a detailed food diary of their food consumption for this period. The final study will take place 6-12 months after the weight loss treatment whilst patients are on their normal diet. Throughout this period, the investigators will be in close contact with those patients who have diabetes to optimise their glucose control through adjustments of their glucose-lowering medications. Our unit has a track record in safe and effective glycaemic management before and after weight loss interventions [17].

Patient will attend the investigation unit after an overnight fast. They will be weighed and an intravenous cannula will be inserted in the antecubital of each arm. The first cannula will be used for infusions and the other for blood sampling. Participants will be asked to provide a urine sample that will be tested for albumin creatinine ratio and metabolic/inflammatory markers. If blood glucose levels are high on arrival an insulin infusion will be started to attain a stable glucose level (4.0 -6.0 mmol/l) prior to commencement of the hyperinsulinaemic euglycaemia clamp (Time -120). A priming dose of a stable isotope tracer will be given directly into the cannula and stable isotope of glucose will be infused at -120 to +120 minutes to measure the rate of hepatic glucose production. At 0 minutes a low dose insulin infusion (0.3-0.5 mU/kg/min) will be commenced and a variable rate infusion of 20% dextrose "spiked" glucose tracer will be given to maintain the glucose level to 4.0-6.0 mmol/l. Blood samples of 4-13 mls each will be taken to measure glucose, insulin, c-peptide, glucagon, lipids and gut hormones at -120, -20, -15, -10, -5, 0, +30, +60, +90, +100, +110, +120, +150. At +120 minutes the insulin infusion and glucose tracer infusion will be stopped. At the same time points participants will be asked to complete appetite visual analogue scales. Participants will be fed and glucose infusion continued for a further 20 minutes to prevent hypoglycaemia. Depending on the patient's blood glucose control on arrival, the maximum duration of the whole visit will be up to 7 hours.

Blood samples will be centrifuged and the separated plasma kept in a - 20°C freezer. The isotopic enrichment of plasma glucose will be determined by gas chromatography mass spectrometry (GCMS) at the Wolfson Centre for Translational Research, Postgraduate Medical School, University of Surrey.

The stable labelled isotope tracers [6,6 ²H₂] is not a drug, but a naturally occurring metabolite which has been labelled with a stable, i.e. non-radioactive label. Stable isotope tracers are widely used in metabolic research by groups throughout the UK and worldwide. All labelled isotope tracers are ordered from Cambridge Isotopes Ltd through their UK suppliers CK gases Ltd. They are prepared as sterile solutions suitable for intravenous use by the Pharmacy Production Unit at Guys & St. Thomas' NHS Trust to ensure they are safe for the participants. The products are supplied with the appropriate

certificate of analysis and MSDS. We have used the same manufacturer to be sure of the quality of the products and the supporting documentation.

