3.1 Study outcome measures

Primary Endpoint

The primary outcome measure will be total energy intake and dietary composition in terms macronutrient proportions (fat, saturated fat, carbohydrates, sugars, fibre, protein and salt).

Secondary outcomes

The secondary outcome measures will be the ratings of hunger and satiety, gut hormones, bile acid and lipid levels before and after a standardised meal. In the clamp studies, the outcome will also be hepatic glucose output and insulin resistance.

4. Participant Entry

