Appendix

[figure not shown]
Table 1: Testing time points

Frequency test performed	Test
Preoperatively	400kcal standard meal plus venous blood sampling and visual analogue scores
Day 2	400kcal standard meal plus venous blood sampling and visual analogue scores
Day 7-30)	400kcal standard meal plus venous blood sampling and visual analogue scores
3 months	400kcal standard meal plus venous blood sampling and visual analogue scores
6-12 months	400kcal standard meal plus venous blood sampling and visual analogue scores

Table 2: Meal study protocol

Time	Intervention	Outcome measured	Outcome measured
0'	400kcal standard meal	Venous blood sampling 5ml	Visual analogue score
15'		Venous blood sampling 5ml	
30'		Venous blood sampling 5ml	
60'		Venous blood sampling 5ml	Visual analogue score
90'		Venous blood sampling 5ml	
120'		Venous blood sampling 5ml	Visual analogue score
150'		Venous blood sampling 5ml	
180'		Venous blood sampling 5ml	Visual analogue score

Diagrammatic representation of the metabolic study protocol

Metabolic study protocol

Time (min)	Action	Blood sampling (volume)			
		Glucose Conc and Enrichment (1ml)	Insulin (Serum) (3ml)	Glucagon (Serum) (2ml)	c-peptide/lipids/Gut hormones (Serum) (7ml)
- 120 to 0		Sliding scale insulin infusion 1 U/ml (0.1 - 6 ml/h) 15 minute interval blood glucose monitoring; maintenance of glucose at 4.0 – 6.0 mmol/l;			
-120		X	X		
-120 to +120		Start 6,6 ² H ₂ glucose infusion			
-20		X	X		
-15		X	X		
-10		X	X		
-5		X	X		
0		X	X	X	X
0-240		Low dose insulin infusion 0.3-0.5 mU/kg/min Initiation of variable infusion of 20% glucose spiked with 2H2 glucose; maintenance of clamp glucose at 4.0 – 6.0 mmol/l			
+30		X	X	X	X
+60		X	X		
+90		X	X	X	X
+100		X	X		
+110		X	X		
+120	Stop isotope and insulin Food will be given to the patient	X	X	X	X
+150		X	X	X	X
.

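### The meal test takes no appetite rating between the meal and 60 minutes, so early differences in hunger and satiety between groups cannot be seen and peaks between the hourly ratings are blunted

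*Combined protocol and SAP*

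**What the plan says.** Section 3 (Study Design) describes a meal test in 20 patients per group, done five times per patient. Blood sampling is fully specified: "5ml blood will be withdrawn at baseline, 15, 30, 60, 90, 120, 150 and 180 minutes following ingestion". For appetite the same section says only "visual analogue scores will be measured over a 3 hour period using previously published methodology" and gives no individual times.

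The times appear only in the Appendix, under "Table 2: Meal study protocol". All eight rows have a blood sample. The score appears in the rows for 0, 60, 120 and 180 minutes. The row at 0 is the meal row: "0' 400kcal standard meal Venous blood sampling 5ml Visual analogue score". The next row has blood alone: "15' Venous blood sampling 5ml". The 30, 90 and 150 minute rows are the same.

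Section 3.1 makes the ratings an outcome: "The secondary outcome measures will be the ratings of hunger and satiety, gut hormones, bile acid and lipid levels before and after a standardised meal". Section 7 applies a t-test to the secondary end points. It does not say which rating, or which summary of the ratings, is to be tested.

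**The concern.** Satiety is in the study objective, and section 1.1 attributes the weight loss after these operations mainly to less hunger and more satiety. It also describes incretin drugs as slowing gastric emptying. So the eight groups may well differ in how quickly satiety rises and fades after a meal. The rating schedule leaves the first 60 of 180 minutes without a post-meal value, although the patient is present and gives blood twice in that time.

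Two things are at stake:

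- **Unequal measurement.** A satiety peak that falls between rated times is recorded too low. Groups whose peaks fall at different times would then be measured with different accuracy, and that difference would pass into any comparison of peak or area.
- **Lost pairing.** Four of the eight hormone values, including both early ones, cannot be set against an appetite rating from the same moment.

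**Working it through.** **The plan's own figures.** The documents give no power, variability or expected time course for the ratings. The meal study's only stated figure is 80% power for PYY. It reproduces as a one-sample normal approximation, Φ((5/8)·√20 − 1.96) = 0.798, and does not bear on the ratings.

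**Counting rows in Appendix Table 2.**

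- Blood: 8 times. Ratings: 4 times, so 4/8 = 50%.
- Strictly between 0 and 60 minutes: 2 blood samples (15, 30), 0 ratings.
- Part of the window before the first post-meal rating: 60/180 = 33%.

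**What the gap can do.** This part rests on assumed curves. Take a satiety score f(t) that rises linearly from 0 to 60 mm at time p and then decays as 60·exp(−(t − p)/90).

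- True area over 0–180 min = 30p + 60·90·(1 − exp(−(180 − p)/90)).
- Four-point area = 60·[f(0)/2 + f(60) + f(120) + f(180)/2].
- Eight-point area = trapezoid rule on the blood times.

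Example with p = 15: f(60) = 60·exp(−45/90) = 36.39, f(120) = 18.68, f(180) = 9.59. The four-point area is 60·(36.39 + 18.68 + 4.80) = 3,592 mm·min. The true area is 450 + 5,400·(1 − exp(−165/90)) = 4,987. The error is 3,592/4,987 − 1 = −28.0%.

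| Peak at (min) | True area (mm·min) | 4-point area | Error | Highest score on 4 points (mm) | 8-point error |
|---|---|---|---|---|---|
| 15 | 4,987 | 3,592 | −28.0% | 36.4 | +0.7% |
| 30 | 5,280 | 4,244 | −19.6% | 43.0 | +0.8% |
| 45 | 5,545 | 5,014 | −9.6% | 50.8 | −3.4% |
| 60 | 5,777 | 5,923 | +2.5% | 60.0 | +0.6% |
| 90 | 6,114 | 5,642 | −7.7% | 43.0 | +0.5% |

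With decay constants of 60 to 120 minutes, the four-point error for 15 and 30 minute peaks ranges from −36% to −17%.

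**Sensitivity to shape.**

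- *Same true area for every peak time* (unit peak, linear rise, linear fall to 0 at 180 min; true area 90). The four-point area is 65.5 (−27%), 72.0 (−20%), 80.0 (−11%), 90.0 (0%) and 80.0 (−11%) for peaks at 15, 30, 45, 60 and 90 minutes. The eight-point area is 90.0 throughout, except 86.7 for the 45-minute peak.
- *Fast rise that is sustained to 180 min.* The true areas are 172.5, 165 and 150 for rises over 15, 30 and 60 minutes. The four-point area is 150 for all three, so the faster group looks equal and its early advantage disappears.

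**How much of a gap between groups is an artefact.** On the first set of curves, the 15-minute group truly has 1 − 4,987/5,777 = 14% less area than the 60-minute group. The four-point schedule shows 1 − 3,592/5,923 = 39%. It widens a real difference and does not create the whole of it.

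**The case against.** **Bias against fast-acting treatments.** A reader might infer that the schedule works against treatments with early satiety while slower groups are measured correctly. The documents give no satiety time course, and the arithmetic does not bear this out as a general statement. On the same curve a 90-minute peak is recorded as 43.0 mm, exactly as a 30-minute peak is. Early satiety that lasts is recorded as equal, not lower. What stands is narrower: a peak between rated times is blunted, the area error is largest for peaks early in the first hour, and early differences are invisible.

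**No planned analysis is broken.** Neither a peak nor an area is specified, and no time-matched analysis of hormones and appetite is planned. A comparison of the ratings at 60, 120 or 180 minutes taken singly would not be distorted. This is correct. It means the consequence depends on a summary still to be chosen, and that the undefined summary is itself a gap.

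**Published method.** Section 3 refers to published methodology, which may rate hourly. That cannot be checked here. Even if it does, precedent would not supply the missing first hour.

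**The clamp study as precedent.** Section 3 says of the clamp "At the same time points participants will be asked to complete appetite visual analogue scales", which is most naturally read as the blood-sampling times. It shows that frequent rating is considered workable, but little more. Those participants are unfed until +120 minutes, only the +150 sample follows food, and the clamp table has no rating column.

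**Table extraction.** The table was read from PDF, but a regular hourly pattern is unlikely to come from a broken column.

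**Conclusion.** The point holds as a cheap improvement to a secondary outcome. It is certain from Appendix Table 2 that no rating is taken between the meal and 60 minutes, and that the 15, 30, 90 and 150 minute hormone values have no paired rating. It follows that differences in early satiety cannot be seen.

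The size of any distortion is not known. On the assumed decaying curves (90-minute constant) the area error runs from −28% to +2.5% according to peak time, against within 1% on eight points, or about −3% for a 45-minute peak. These figures rest on the assumed shape and on area being the summary. They do not establish a bias in a known direction between any two of the study's groups. Total energy intake and macronutrient composition, the primary outcome, are unaffected.

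**What to change.** 1. In Appendix Table 2, add the visual analogue score to the 15, 30, 90 and 150 minute rows. The 15 and 30 minute ratings matter most. State the rating times in section 3 as well.
2. In section 7, name the summary of the hunger and satiety ratings to be compared, for example the area over 0–180 minutes.
3. For any patient whose baseline test used the hourly schedule, analyse the 0, 60, 120 and 180 minute ratings at all visits, so that comparisons before and after intervention use the same times. Where a comparison between groups includes such patients, use those four times for everyone in it.

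**Cost.** Four more short rating forms per meal test, at times when the patient is already giving blood. No extra visit, sample or staff is needed. Patients already started contribute only to the reduced common schedule. Ratings not taken at the time cannot be recovered later.

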3.1 Study outcome measures

Primary Endpoint

The primary outcome measure will be total energy intake and dietary composition in terms macronutrient proportions (fat, saturated fat, carbohydrates, sugars, fibre, protein and salt).

Secondary outcomes

The secondary outcome measures will be the ratings of hunger and satiety, gut hormones, bile acid and lipid levels before and after a standardised meal. In the clamp studies, the outcome will also be hepatic glucose output and insulin resistance.

4. Participant Entry

4.1 Inclusion criteria

Adult patients with overweight or obesity (BMI ≥ 30 Kg/m 2) who are having a weight loss intervention.

4.2 Exclusion criteria

None.

5. Adverse events

5.1 Definitions

Adverse Event (AE): any untoward medical occurrence in a patient or clinical study subject.

Serious Adverse Event (SAE): any untoward and unexpected medical occurrence or effect that:

- **Results in death**
- **Is life-threatening** – *refers to an event in which the subject was at risk of death at the time of the event; it does not refer to an event which hypothetically might have caused death if it were more severe*
- **Requires hospitalisation, or prolongation of existing inpatients' hospitalisation**
- **Results in persistent or significant disability or incapacity**
- **Is a congenital anomaly or birth defect**

Medical judgement should be exercised in deciding whether an AE is serious in other situations. Important AEs that are not immediately life-threatening or do not result in death or hospitalisation but may jeopardise the subject or may require intervention to prevent one of the other outcomes listed in the definition above, should also be considered serious.

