5.3 Reporting procedures

All adverse events should be reported. Depending on the nature of the event the reporting procedures below should be followed. Any questions concerning adverse event reporting should be directed to the Chief Investigator in the first instance.

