5.3.1 Non serious AEs

All such events, whether expected or not, should be recorded.

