5.3.2 Serious AEs

An SAE form should be completed and faxed to the Chief Investigator within 24 hours. However, relapse and death due to non-obesity or diabetes related causes, and hospitalisations for elective treatment of a pre-existing condition do not need reporting as SAEs. All SAEs should be reported to the Charing Cross Hospital REC where in the opinion of the Chief Investigator, the event was:

- 'related', i.e. resulted from the administration of any of the research procedures; and
- 'unexpected', i.e. an event that is not listed in the protocol as an expected occurrence

Reports of related and unexpected SAEs should be submitted within 15 days of the Chief Investigator becoming aware of the event, using the NRES SAE form for non-IMP studies. Local investigators should report any SAEs as required by their Local Research Ethics Committee, Sponsor and/or Research & Development Office.

Contact details for reporting SAEs

[contact], attention [name] [name]

Please send SAE forms to: [name] [name], Imperial Weight Centre, [name].

[contact] (Mon to Fri 09.00 – 17.00)

6. Assessment and Follow Up

Assessment will take place through the use of dietary assessments, standardized meal tests and metabolic clamp tests. The dietary assessments will be completed once before and 1, 3, 6 and 12 months post all interventions. The meal tests will take place once before and 2 days, 7-30 days, 3 and 12 months after intervention. The metabolic study will be performed 4 times: at baseline, within 1-2 weeks of a low calorie diet and within 1-2 weeks after their weight loss treatment, whilst on the same liquid diet. The final study visit will take place 6-12 months after the weight loss treatment whilst patients are on their normal diet.

7. Statistics and Data Analysis

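### Section 5.1 makes unexpectedness a condition of being an SAE, which conflicts with section 5.3.2 and can take expected serious events out of expedited review

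*Combined protocol and SAP*

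**What the plan says.** Section 5.1 defines an adverse event (AE) as "any untoward medical occurrence in a patient or clinical study subject", with no condition on expectedness. It defines an SAE as "any untoward and unexpected medical occurrence or effect that" meets one of five criteria: death, threat to life, hospitalisation or its prolongation, lasting disability, or congenital anomaly. A closing paragraph asks for medical judgement in other cases and extends seriousness to "Important AEs that are not immediately life-threatening or do not result in death or hospitalisation but may jeopardise the subject". That extension carries no condition on expectedness either.

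The reporting rules follow in section 5.3. The general rule is "All adverse events should be reported". For non-serious events, 5.3.1 says: "All such events, whether expected or not, should be recorded". For serious events, 5.3.2 says: "An SAE form should be completed and faxed to the Chief Investigator within 24 hours". It then sends to the ethics committee those SAEs that the Chief Investigator judges both related to a research procedure and unexpected, the latter meaning "an event that is not listed in the protocol as an expected occurrence". The committee deadline is stated as "Reports of related and unexpected SAEs should be submitted within 15 days" of the Chief Investigator becoming aware.

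**The concern.** Seriousness describes the outcome of an event. Expectedness describes whether the event was foreseen. Section 5.1 merges the two. The 24-hour form and the opinion on relatedness both depend on SAE status, so an event that fails the definition because a site foresaw it loses both, however grave its outcome.

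What is at stake is safety oversight. In groups that receive surgery, an implanted device, drugs or a clamp procedure, some serious complications are foreseeable, and the Chief Investigator should hear of them promptly. Sites may also apply the word differently, because 5.1 does not say what *unexpected* means.

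**Working it through.** The protocol gives no SAE figure to reproduce, so the check is a comparison of the sections.

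**1. Follow three kinds of event through the text as written.**

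- *Life-threatening and unforeseen.* It meets 5.1, so it is an SAE. The 24-hour form is due, the Chief Investigator gives an opinion, and the committee is told if the event is related.
- *Life-threatening, but foreseen in the site's view.* It fails 5.1 on the word *unexpected*. Section 5.3.2 then does not apply. Section 5.3.1 does not fit either, because its heading limits it to non-serious events. Only the general rule in 5.3 remains, and that sets no deadline and no review of relatedness.
- *Foreseen and less grave, but putting the patient at risk.* The medical-judgement paragraph makes it serious without asking about expectedness.

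So a foreseen lesser event can be serious while a foreseen life-threatening one is not. That ordering cannot be intended.

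**2. Compare the two uses of *unexpected*.** If the word means the same in both sections, every SAE is already unexpected under 5.1, and the second condition in 5.3.2 removes nothing. If that condition does some work, expected SAEs must exist, and 5.1 has excluded them. Either way the sections need reconciling.

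**3. Look for the list.** Section 5.3.2 relies on events listed as expected in the protocol. No such list is in the available text. The background section mentions nausea with incretin therapies, but as a mechanism of reduced food intake. The section numbering runs from 5.1 to 5.3. This may be only a numbering slip, but it is a reason to say that the list is not in the available text rather than that it never existed.

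**4. Trace the effect of the missing list.**

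- *If the 5.3.2 meaning is carried back to 5.1:* nothing is listed, so nothing is expected, and the definition excludes 0 events.
- *If sites use ordinary clinical expectation in 5.1:* every serious event that they foresaw is excluded. Take a serious hypoglycaemic episode around the clamp. Section 3 continues glucose after the clamp to prevent hypoglycaemia, so a site could call the episode expected and file no form. Yet it is unlisted, hence unexpected under 5.3.2, and reportable to the committee if related. The 5.1 wording would block a report that 5.3.2 is written to require.

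**5. Size.** The documents give no complication rate and no share of complications that are expected. As an illustration on an assumed rate only: if 2% to 10% of a group of 50 had a serious event regarded as expected, 0.02 × 50 = 1 to 0.10 × 50 = 5 events in that group would fall outside the literal definition. Under the first reading in step 4 the number is 0.

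**The case against.** The strongest reply is that the only meaning of *unexpected* in the protocol is the one in 5.3.2. With no list, that meaning excludes nothing. Section 5.3 also requires all adverse events to be reported, and the committee filter shows that the authors thought expected SAEs exist. Read as a whole, section 5 could be taken to treat expected serious events as SAEs.

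Part of this stands. It shows that loss of events is possible rather than certain, and that the likely harm is misclassification or delay. It does not rescue the definition. The 5.3.2 meaning is given only within the committee criteria, 5.1 does not refer to it, and the general reporting rule does not replace a 24-hour form.

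A reader might go further and infer any of the following. The documents do not support them.

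- *Serious events are under-counted mainly in the surgical and device groups.* More foreseeable complications in Groups A to D than in lifestyle Group G is a reasonable guess, but no rates are given. Control Group H also has surgery or endoscopy.
- *A comparison of SAEs between groups would be biased by a known amount.* If shares eA and eH of serious events are called expected in an invasive and a control group, the reported ratio is the true ratio × (1 − eA)/(1 − eH). With an assumed true ratio of 2, eA = 0.8 and eH = 0.1 give 2 × 0.2/0.9 = 0.44, and eA = 0.5 and eH = 0.2 give 2 × 0.5/0.8 = 1.25. Equal shares give back 2. The answer comes entirely from the assumed shares. Adverse events are not an outcome in section 3.1, and section 7 plans no SAE comparison.
- *The Chief Investigator never learns of these events.* Section 5.3 still requires them to be reported. What is lost is the expedited route and the opinion on relatedness attached to it. Relatedness in 5.3.2 also concerns research procedures, and in this observational study most complications of the treatments themselves would not qualify.

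**Conclusion.** The definition in 5.1 is wrong as written and contradicts 5.3.2. Read literally, a serious event that a site considers expected needs no 24-hour form and no opinion on relatedness. The list on which 5.3.2 depends is not in the available text, so what 5.1 excludes turns on each site's reading.

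The definitional conflict rests on the text alone and needs no assumption. The practical effect depends on how sites read the word: from no events, if they apply the 5.3.2 meaning, to every foreseen serious event, if they apply clinical expectation. Neither the number nor its distribution over Groups A to H can be derived. This is a safety-reporting defect that should be corrected. It does not touch the planned dietary, meal-test or clamp analyses.

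**What to change.** 1. In the 5.1 SAE definition, delete the words *and unexpected*, so that seriousness alone decides SAE status.
2. Keep expectedness only in the 5.3.2 test for committee reporting.
3. Add the list of expected events to which 5.3.2 refers, or point to where it is. Without it the retained filter has nothing to work from.

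The cost is two deleted words, the drafting of a list, and more SAE forms. The exemption in 5.3.2 for elective admissions for a pre-existing condition stays in place, which limits the extra forms.

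Committee reporting may not stay the same. Until the list exists, any related event newly classed as an SAE counts as unexpected under 5.3.2 and goes to the committee. Some additional reports are therefore possible, and adding the list at the same time would limit them to events that it does not cover.
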